Measure	Variable	Analysis Method (Section 4.2.3)	Population (Section 4.2.1)	Comparison/Time Point	Analysis Type
		Logistic Regression using NRI a	FAS (Severe/very severe SALT subgroups c among patients with ClinRO Measure for EL Hair Loss $\geq 2$ at Baseline)	Bari 4-mg dose or Bari 2-mg dose vs PBO at Week 36;	Dosing evaluation analysis
		Logistic Regression using NRI a	FAS (Duration of current AA episode < 4 years / $\geq 4$ years subgroups d among patients with ClinRO Measure for EL Hair Loss $\geq 2$ at Baseline)	Bari 4-mg dose or Bari 2-mg dose vs PBO at Week 36;	Dosing evaluation analysis
Clinician-Reported Outcome (ClinRO) for Nail Appearance	Proportion of patients achieving ClinRO Measure for Nail Appearance 0 or 1 with a $\geq 2$ -point improvement from Baseline	Logistic Regression using NRI a	FAS (among patients with ClinRO Measure for Nail Appearance $\geq 2$ at Baseline)	Bari 4-mg dose or Bari 2-mg dose vs PBO at Weeks 24 and 36;	Exploratory analysis

a Primary censoring rule.

b Secondary censoring rule.

c Severe SALT subgroup = patients with SALT score of 50%-94% at baseline; Very severe SALT subgroup = patients with SALT score of 95%-100% at baseline.

d Duration of current AA episode < 4 years subgroup = patients with duration of current AA episode at baseline < 4 years; Duration of current AA episode  $\geq 4$  years subgroup = patients with duration of current AA episode at baseline  $\geq 4$  years.

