To compare the maintenance of efficacy for patients randomized to remain on baricitinib, compared with patients randomized to placebo at Week 52 of the long-term extension period, as measured by physician-assessed signs of AA	
 
• Proportion of patients maintaining SALT <math>\leq 20</math> at Weeks 64, 76, 88, 104, 120, 136, 152, 168, 184, and 200
 
• Proportion of patients experiencing a loss of treatment benefit (<math>>20</math>-point absolute
 

	
worsening in SALT score) at Weeks 64, 76, 88, 104, 120, 136, 152, 168, 184, and 200.
 
 
Time to loss of treatment benefit (>20-point absolute worsening in SALT score)
 

For patients experiencing loss of treatment benefit after randomization to placebo at Week 52:
 
 
To evaluate the recapture of efficacy for patients who were retreated after experiencing a loss of treatment benefit during the long-term maintenance period as measured by physician-assessed signs of AA
 
To evaluate the recapture of efficacy for patients who were retreated after experiencing a loss of treatment benefit during the long-term maintenance period as assessed by PRO and quality of life tools
 
	
 
Proportion of patients that achieve a SALT <math>\leq 20</math> at 12, 16, 24, and 36 weeks of retreatment with baricitinib
 
Percent change in SALT score at 12, 16, 24, and 36 weeks of retreatment with baricitinib
 
Proportion of patients with a PRO for Scalp Hair Assessment score of 0 or 1 at 12, 16, 24, and 36 weeks of retreatment with baricitinib
 

Abbreviations: AA = alopecia areata; ClinRO = clinician-reported outcome; EB = eyebrow; EL = eyelash; HADS = Hospital Anxiety and Depression Scale; PRO = patient-reported outcome; SALT = Severity of Alopecia Tool; SALT50 = at least 50% improvement from Baseline in SALT score; SALT75 = at least 75% improvement from Baseline in SALT score; SALT90 = at least 90% improvement from Baseline in SALT score; SALT100 = 100% improvement from Baseline in SALT score.

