Patients who achieve a SALT  $\leq 20$  at Week 52 (responders) AND who have remained on the same dose of baricitinib from randomization (Visit 2) to Week 52, will enter the randomized withdrawal, which is meant to evaluate the change in clinical response after treatment withdrawal, and does not account for whether the sample size is sufficient to detect statistical difference between baricitinib and placebo. It is expected that there would be approximately 100 patients eligible for the randomized withdrawal.

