Uptitration Population	All patients who are randomized to baricitinib 2-mg at baseline having SALT score >20 at Week 52 and were rescued to baricitinib 4-mg dose at Week 52. All patients need to take at least one dose of treatment and have non-missing SALT score on or after Week 52.
Retreated Population	A subset of patients who enter randomized withdrawal (randomized to placebo at Week 52) and were retreated with their baseline baricitinib dose at any time after experiencing loss of treatment benefit (SALT>20).
Safety Population	The safety population is defined as all randomized patients who receive at least 1 dose of investigational product (IP) and who did not discontinue from the study for the reason 'Lost to Follow-up' at the first postbaseline visit. Patients will be analyzed according to the IP to which they were assigned.

Abbreviations: AGA = androgenetic alopecia; GCP = good clinical practice; IP = investigational product.

a Some male patients with Grade IV AGA and female patients with patterned baldness may only be identified after hair regrowth on the scalp.

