#### **4.2.2. Definition of Baseline and Postbaseline Measures**

The baseline utilized in the efficacy analyses depends on the analysis being performed. The baseline value for the efficacy and health outcome analyses for all populations is defined as the last non-missing measurement on or prior to the date of first study drug administration (expected at Week 0, Visit 2) unless otherwise stated. If a patient is randomized but does not receive study drug, then the date of randomization is used instead of the first dose date. The efficacy and health outcome analyses for the randomized withdrawal population will use the measurement on or immediate prior to the date of Visit 2 (Week 0) or date of visit 11 (Week 52) as baseline as appropriate for the endpoints, unless otherwise stated. The efficacy and health outcome analyses for the retreated population will use the measurement on or prior to the date when patients got retreated.

Baseline for the safety analyses is defined as the last non-missing scheduled (planned) measurement on or prior to the date of first study drug administration for continuous measures by-visit analyses, unless otherwise stated, and all non-missing measurements on or prior to the date of first study drug administration for all other analyses.

Postbaseline measurements are collected after study drug administration through Week 200 (Visit 24) or early discontinuation visit. For data collected in the electronic Clinical Outcomes Assessment (eCOA) tablet (including Patient-Reported Outcomes [PRO] and Clinician-Reported Outcomes [ClinRO]) and related to efficacy assessments, unscheduled postbaseline visits that fall within the visit windows defined by Lilly will be summarized in the by-visit analyses if there is no scheduled visit available. Refer to clinical protocol I4V-MC-JAHO(e) for detail of the visit windows. If there is more than 1 unscheduled visit within the defined visit window and no scheduled visit is available, the unscheduled visit closest to the scheduled visit date will be used. If 2 unscheduled visits of equal distance are available, then the latter of the 2 will be used.

Postbaseline measures for the safety analyses are defined as the non-missing scheduled (planned) measurements after the date of first study drug administration for continuous measures by-visit analyses and all non-missing measurements after the date of first study drug administration for all other analyses.

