		SALT 100	Improvement in Baseline =100% % change from Baseline = -100	Missing if Baseline or observed value is missing

Measure	Description	Variable	Derivation/Comment	Imputation Approach if with Missing Components
		$SALT \leq 20$	Observed SALT score $\leq 20$	Missing if observed value is missing
		Absolute SALT score $\leq 10$	Observed SALT score $\leq 10$	Missing if observed value is missing
		Time to achieve $SALT \leq 20$	Date of visit for first time achieving $SALT \leq 20$ – randomization date at Visit 2	Censored at the last SALT collection date, scheduled visit date or ETV date during the blind treatment period, whichever is the latest and applicable
		With loss of treatment benefit in SALT from Week 52	Observed SALT score post Week 52 visit – observed SALT score at Week 52 $> 20$	Missing if any of these two observed values is missing.
		Without loss of treatment benefit in SALT from Week 52	Observed SALT score post Week 52 visit – observed SALT score at Week 52 $\leq 20$	Missing if any of these two observed values is missing.
Patient-Reported Outcome (PRO) for Scalp Hair Assessment	It's a novel patient-reported outcome (PRO) assessment of the patient's current extent of scalp involvement. Like the AA-IGA, it is comprised of 5 category response options: 0 = No missing hair (0% of my scalp is missing	PRO for Scalp Hair Assessment score	Single item. Range: 0 to 4	Single items, missing if missing.
		PRO for Scalp Hair Assessment score of 0 or 1	Observed score of 0 or 1	Single items, missing if missing.

Measure	Description	Variable	Derivation/Comment	Imputation Approach if with Missing Components
	hair; I have a full head of hair); 1 = A limited area (1%-20% of my scalp is missing hair); 2 = A moderate area (21%-49% of my scalp is missing hair); 3 = A large area (50%-94% of my scalp is missing hair); and 4 = Nearly all or all (95%-100% of my scalp is missing hair).	PRO for Scalp Hair Assessment score of 0 or 1 with a $\geq 2$ -point improvement from baseline	Observed score of 0 or 1 and change from baseline $\leq -2$	Missing if Baseline or observed value is missing.

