**Table JAHO.4.8. Description of Analysis Beyond Week 36 Placebo-Controlled Period**

Measure	Variable	Analysis Method (Section 4.2.3)	Population (Section 4.2.1)	Comparison/Time Point	Analysis Type
Severity of Alopecia Tool (SALT)	Proportion of patients maintaining SALT $\leq 20$	Descriptive	Randomized Withdrawal Population	Summary statistics will be provided at each post-baseline visit during the Long-Term Extension and Bridging Long-Term Extension Period	Other Secondary
	Proportion of patients with >20-point absolute worsening in SALT score	Descriptive	Randomized Withdrawal Population	Summary statistics will be provided at each post-baseline visit during the Long-Term Extension and Bridging Long-Term Extension Period	Other Secondary
	Time to >20-point absolute worsening in SALT score	Kaplan-Meier Plot	Randomized Withdrawal Population	Summary statistics will be provided at each post-baseline visit during the Long-Term extension and Bridging Long-Term Extension Period.	Other secondary
	Proportion of patients achieving SALT $\leq 20$	Descriptive	Retreated Population	Summary statistics will be provided at Weeks 12, 16, 24, and 36 of retreatment with baricitinib	Other secondary
	Percent change in SALT score	Descriptive	Retreated Population	Summary statistics will be provided at Weeks 12, 16, 24, and 36 of retreatment with baricitinib	Other secondary
PRO for Scalp Hair Assessment	Proportion of patients with a PRO for Scalp Hair Assessment score of 0 or 1	Descriptive	Retreated Population	Summary statistics will be provided at Weeks 12, 16, 24, and 36 weeks of retreatment with baricitinib	Other secondary

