**Table JAHO.4.11 Description of Primary, Secondary and Exploratory Efficacy Analyses**

Measure	Variable	Analysis Method (Section 4.2.3)	Censoring Rule	Population (Section 4.2.1)	Time Point
	Time to achieve SALT $\leq 20$	
 
Descriptive
 
Kaplan-Meier plot
 
	Secondary Censoring Rule	Retreated Population	Week 52 - 200
	Time to loss of treatment benefit (>20-point absolute worsening in SALT score)	
 
Descriptive
 
Kaplan-Meier plot
 
	Tertiary Censoring Rule	Randomized Withdrawal Population	Week 52 - 200
	Proportion of patients achieving an absolute SALT $\leq 10$	Descriptive using Obs and mLOCF	Tertiary Censoring Rule	Randomized Withdrawal Population	Weeks 52-200
		Descriptive using Obs and mLOCF	Secondary Censoring Rule	Uptitration Population	Weeks 52-200
		Descriptive using Obs	Secondary Censoring Rule	Retreated Population	Weeks 52-200
	Proportion of patients with loss of benefit in SALT	Descriptive using Obs and mLOCF	Tertiary Censoring Rule	Randomized Withdrawal Population	Weeks 52-200
	Proportion of patients without loss of benefit in SALT	Descriptive using Obs and mLOCF	Tertiary Censoring Rule	Randomized Withdrawal Population	Weeks 52-200

Measure	Variable	Analysis Method (Section 4.2.3)	Censoring Rule	Population (Section 4.2.1)	Time Point
	SALT Change and Percent Change from baseline	Descriptive using Obs and mLOCF	Tertiary Censoring Rule	Randomized Withdrawal Population	Weeks 52-200
		Descriptive using Obs and mLOCF	Secondary Censoring Rule	Uptitration Population	Weeks 52-200

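### Time to SALT ≤20 in the Retreated Population at the final lock has only a Visit 2 time origin, which places every event before retreatment

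*SAP*

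**What the plan says.** The protocol supplied is the open-label addendum, which has no withdrawal or retreatment, so the SAP is the only source on this point.

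- **Derivation.** SAP section 4.11 names Table JAHO.4.6 as the place for efficacy outcome derivations. Time to SALT ≤20 is there the date of the first visit with SALT ≤20 minus the "randomization date at Visit 2". Patients without the event are censored at the last SALT, scheduled visit or "ETV date during the blind treatment period, whichever is the latest and applicable".
- **Final-lock use.** Table JAHO.4.11 lists time to SALT ≤20 for the Retreated Population, descriptive and Kaplan-Meier, under the secondary censoring rule, over study Weeks 52 to 200. No other origin is given.
- **Who is in the population.** Section 4.1 admits to randomized withdrawal patients with SALT ≤20 "at Week 52 (responders) AND who have remained on the same dose of baricitinib". Table JAHO.4.1 defines the Retreated Population as those of them who were randomized to placebo at Week 52 and "were retreated with their baseline baricitinib dose at any time after experiencing loss of treatment benefit (SALT>20".
- **Where the SAP does use a retreatment clock.** The objectives in section 2.2 are set "at 12, 16, 24, and 36 weeks of retreatment with baricitinib". Table JAHO.4.8 states: "Summary statistics will be provided at Weeks 12, 16, 24, and 36 of retreatment with baricitinib". Table JAHO.4.9 also counts from retreatment. Section 4.2.2 says: "The efficacy and health outcome analyses for the retreated population will use the measurement on or prior to the date when patients got retreated".
- **By-visit rows.** The final-lock Retreated rows for the proportions with SALT ≤20 (Table JAHO.4.10) and SALT ≤10 (Table JAHO.4.11) use observed data at study Weeks 52 to 200.

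**The concern.** The row is meant to show how quickly patients regain response once baricitinib is restarted. The derivation it inherits suits the placebo-controlled comparison, where everyone starts above SALT 20 at Visit 2. In the Retreated Population, qualifying for membership already requires having had the event. A program that follows Table JAHO.4.6 would produce a curve showing complete and early recapture that carries no information about retreatment. A reader of the report could take it for a favourable result.

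A milder version affects the two SALT proportion rows. Patients relapse and restart at different times, so one study week combines patients still on placebo with patients retreated for different lengths of time.

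**Working it through.** The SAP gives no sample size, power or expected rate for the Retreated Population, so there is no planned figure to reproduce. The check is one of logic, with an illustration.

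**1. Where the event falls under the stated rule.** Let F be the week of the first SALT ≤20 and R the week of retreatment, both counted from Visit 2.

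- Entry to randomized withdrawal requires SALT ≤20 at Week 52, so F ≤ 52.
- Retreatment follows randomization to placebo at Week 52 and a later loss of benefit, so R > 52.
- Hence F < R for every member. The derived time is F, and the event fraction is 100% at any true recapture rate.

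**2. Whether other text changes this.**

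- The secondary censoring rule (section 4.4) removes data after permanent discontinuation of study drug. It removes nothing before retreatment.
- The section 4.2.2 sentence fixes a baseline measurement, not a time origin.
- If the Weeks 52 to 200 window is read as moving the origin to Week 52, SALT is ≤20 at that visit and every time is zero.
- If the Week 52 visit itself is left out, a patient still at SALT ≤20 on placebo at Week 64 has the event there, again before retreatment.
- If only events after retreatment are counted but the Visit 2 origin stays, every time includes more than 52 weeks that precede retreatment.

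**3. With a retreatment origin.** Loss of benefit is described as SALT >20 in Table JAHO.4.1 and as worsening by more than 20 points elsewhere in the SAP. A score cannot be below 0, so either description puts SALT above 20 at relapse. Patients therefore start event-free, and the first SALT ≤20 after restart is a true recapture.

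A simulation of 20,000 patients compared the two origins. Its assumptions are mine: first response at Weeks 16 to 52; retreatment equally likely at Weeks 64, 76, 88 or 104; recapture with probability r, equally likely 12, 16, 24 or 36 weeks later.

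| True recapture rate r | Event fraction, Visit 2 origin | Event fraction, retreatment origin |
|---|---|---|
| 0% | 100% | 0% |
| 30% | 100% | 30% |
| 60% | 100% | 60% |
| 90% | 100% | 90% |

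**4. The by-visit proportions.** SALT ≤20 in Table JAHO.4.6 is scored from the value observed at the visit, so these rows are not fixed at 100%. I use the same assumptions and also treat patients as responders until the retreatment visit.

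- Week 52: 100%.
- Week 76: half are not yet retreated. Of the quarter retreated at Week 64, a fraction r/4 has recaptured by 12 weeks. The proportion is 1/2 + (1/4)(r/4) = 1/2 + r/16, which is 50% at r = 0 and 56% at r = 0.9.
- Week 104: the shares of recaptures already seen are 1, 3/4, 1/2 and 0 for retreatment at Weeks 64, 76, 88 and 104. The proportion is r(1 + 3/4 + 1/2 + 0)/4 = 9r/16, which is 0%, 17%, 34% and 51% for r = 0, 0.3, 0.6 and 0.9.
- Week 200: the last possible recapture is at 104 + 36 = 140 weeks, so the proportion equals r.

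The simulation agrees with these figures to within about one percentage point. The early visits say little about recapture, and the late ones recover it in this example.

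**5. Size.** About 100 patients are expected to be eligible (section 4.1). The allocation is 3:1 in favour of staying on baricitinib (footnotes to Figure JAHO.3.2). So 100 × 1/4 = about 25 go to placebo, and at most about 25 are retreated.

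**6. Why the final lock matters.** Table JAHO.4.9 stops at Week 104, and 104 − 36 = 68. A patient retreated at Week 76 has 28 weeks of retreatment by then, and one retreated at Week 88 has 16. Complete 36-week data for most patients come only at a later lock.

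**The case against.** The best defence is that the Table JAHO.4.6 derivation was plainly written for the placebo-controlled endpoint. It counts from randomization, censors in the blind period, and matches the row in Table JAHO.4.7 that runs up to Week 36. Events by Week 52 sit badly with a window of Weeks 52 to 200, so a sensible programmer would probably count from retreatment. That is fair as a guess at intent. It does not remove the problem: the SAP gives one rule for this variable, that rule yields a meaningless result here, and nothing in the SAP states the replacement.

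Two stronger readings are tempting, and the SAP supports neither.

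- A reader might infer that recapture cannot be measured at all. It can. The objective, Table JAHO.4.8 and Table JAHO.4.9 summarize it by weeks of retreatment, and section 4.2.1.1 places Retreated Population efficacy analyses at the final lock.
- A reader might infer that every final-lock analysis of this population counts all patients as responders. Only the time-to-event row does. The SALT proportions use the score at each visit. The PRO for Scalp Hair Assessment and the eyebrow and eyelash ClinRO rows are restricted to response after retreatment. Table JAHO.4.13 has no Retreated row.

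It also stands that these are descriptive analyses of other secondary endpoints, outside multiplicity control, in few patients.

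**Conclusion.** The point holds for one row. As derived, time to SALT ≤20 in the Retreated Population returns an event for 100% of patients, always before retreatment, whatever the true recapture rate. This follows from the definitions and does not depend on the simulation. It assumes that nobody entered randomized withdrawal without SALT ≤20 at Week 52, and that no document outside those reviewed, such as the main protocol, supplies another derivation.

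The lesser point is that the final-lock Retreated rows for the SALT ≤20 and SALT ≤10 proportions blur recapture by mixing time before retreatment with different lengths of retreatment. How much depends on when patients restart, which the SAP does not give, so the percentages by week are illustrative only.

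At most about 25 patients are affected, no confirmatory conclusion is touched, and recapture remains planned elsewhere. The correction is still worth making before the final lock, because the rule as stated gives a wrong and flattering answer.

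**What to change.** In Table JAHO.4.6, add a separate derivation for the Retreated Population and refer to it from the Table JAHO.4.11 row:

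- time zero: date of the first dose of retreatment;
- event: first visit after that date with SALT ≤20;
- censoring: date of the last SALT on retreatment, under the secondary censoring rule.

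For the Retreated rows on the proportions with SALT ≤20 (Table JAHO.4.10) and SALT ≤10 (Table JAHO.4.11), replace study weeks with 12, 16, 24 and 36 weeks of retreatment, as in the objective and Table JAHO.4.8, and show the number of patients contributing at each time point. A display by study week can be kept as an addition if it is labelled as such.

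The cost is a few lines of SAP text and re-indexing visits to the retreatment date. No new data are needed.

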#### **4.11.1. Primary Outcome and Methodology**

The primary analysis of the Phase 3 portion of this study is to test the hypothesis that the 4-mg dose or 2-mg dose of baricitinib is superior to placebo in the treatment of patients with severe or very severe Alopecia Areata (AA), as assessed by the proportion of patients achieving SALT $\leq$  20 at Week 36 using the FAS population, assuming that treatment response disappears at the visits conducted remotely due to COVID-19 or after the patient discontinued study or study treatment. This will serve as the primary estimand. In this estimand, missing data due to the application of the primary censoring rule and the occurrence of other non-censor intercurrent events will be imputed using the NRI method described in Section 4.4.1.

A logistic regression analysis as described in Section 4.2.3 will be used for the comparisons. The odds ratio, the corresponding 95% CIs and p-value, as well as the treatment differences and the corresponding 95% CIs, will be reported. In the case when Firth's correction still results in quasi-separation, Fisher's exact test will be used for primary analysis.

#### **4.11.2. Secondary and Exploratory Outcome Analyses**

Multiplicity controlled analyses will be performed on the primary and key secondary (see Sections 2.1 and 2.2) objectives for the Phase 3 portion of this study in order to control the overall family-wise Type I error rate at a 2-sided alpha level of 0.05. A graphical multiple testing procedure described in Bretz et al. (2011) will be used to perform the multiplicity controlled analyses as described in Section 4.6.

There will be no adjustment for multiple comparisons for any other analyses. The secondary and exploratory efficacy analyses are detailed in Table JAHO.4.7. Health Outcomes/Health-related Quality-of-Life analyses are described in Section 4.11.3.

